3 STUDY DESIGN

This is a Phase 2b randomized, double-blind, placebo-controlled study designed to evaluate the efficacy, safety, PK, and tolerability of BG00011 in subjects with IPF. Approximately 290 subjects who meet inclusion/exclusion criteria will be stratified by background therapy status (subjects receiving background therapy and subjects not receiving background therapy) and randomized in a 1:1 ratio of BG00011 to placebo (**Error! Reference source not found. of the protocol**).

Subjects will receive weekly injections of BG00011 or placebo for 52 consecutive weeks (a total of 52 doses). Study duration for an individual subject is approximately 65 weeks, including a Screening Visit up to 5 weeks prior to the first dose of study treatment, a Placebo-Controlled Treatment Period of 52 weeks, and a Safety Follow-Up Visit 8 weeks after the end of the Treatment Period.

A schematic of the study design is provided in Figure 1. Additional details on the study design and the schedule of study assessment is provided in the full protocol. Due to the early termination of the study, no interim analysis will be performed. This change supersedes the interim analysis planned in the schematic of the study design in the protocol.

Figure 1: Schematic for Study 203PF203

4 SAMPLE SIZE JUSTIFICATION

The sample size calculation is based on the annual declining rate in FVC (mL/year). With 145 subjects randomized per arm, and assuming a 15% dropout rate over a 1-year treatment period, the study has approximately 80% power to show that the BG00011 treatment arms differentiate from the arm without BG00011 at a 2-sided 15% α level, given a treatment effect of 82.5 mL/year with a common standard deviation of 280 mL. The calculation is based on the assumption that the FVC decline rate in subjects receiving placebo and no background therapy is 220 mL/year, and in subjects receiving background but no BG00011 therapy it is assumed to be 110 mL/year. A 60% reduction in the FVC decline rate in the subjects receiving placebo would be a treatment effect of 132 mL/year. A 30% reduction in the FVC decline rate in subjects receiving background therapy would be a treatment effect of 33 mL/year. With the assumption that 50% of each type of subject are randomized in the study, the combined treatment effect is approximately 82.5 mL/year. The 15% dropout rate for this study was estimated based on prior experience for the placebo arms in the Phase 3 studies for nintedanib and pirfenidone [King 2014; Richeldi 2014].

5 ANALYSIS POPULATIONS

5.1 Modified Intent-to-Treat (MITT) Population

The modified intent-to-treatment (MITT) population will include all subjects who are randomized and receive at least 1 dose of study treatment (BG00011 or placebo). Subject will be analyzed by randomized treatment, even if the subject did not receive the assigned treatment or did not follow the protocol until completion. The definition of MITT population is same as the intent-to-treat (ITT) population stated in the protocol.

5.2 Safety Population

The safety population will include the same subjects as defined for the MITT population. However, subjects will be analyzed by actual treatment received. If all subjects take the treatment as they were randomly assigned to, the safety population will be the same as the MITT population.

5.3 Immunogenicity population

The analysis population for immunogenicity is defined as all MITT subjects who have at least 1 postdose immunogenicity sample evaluated for anti-BG00011 antibodies and whose pre-dose anti-BG00011 samples are screened negative at baseline (Day 0) visit.

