16.7. Immunogenicity Data

16.7.1. Analysis Population

The analysis population for immunogenicity is defined as all subjects who were randomized and received at least 1 dose of study treatment and who have at least 1 postdose immunogenicity sample evaluated for anti-BG00011 antibodies.

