1 INTRODUCTION

The intent of this document is to provide guidance for analyses of data for this Phase 2b study. This statistical analysis plan (SAP) has been developed after review of the Clinical Study Protocol 203PF203 (version 1 dated 20NOV2017).

On 16 August 2019, the BG00011 independent Data Safety and Monitoring Board (DSMB) met for a routinely scheduled bi-monthly meeting. During that meeting the DSMB recommended that study 203PF203 be stopped due to an imbalance in the prespecified safety composite endpoint. A separate unblinded team at Biogen has reviewed the data and accepted the DSMB recommendation. Because of the study early termination, the version 2 protocol dated on 02 JULY 2019 was not implemented, it is not used as reference for developing this SAP.

As the study was stopped early, all endpoints will be analyzed and summarized by descriptive statistics only with exception of primary and key secondary efficacy endpoints (i.e. Percent Predicted FVC, Absolute DLco corrected for hemoglobin and Percent Predicted Absolute DLco corrected for hemoglobin). The safety data will be analyzed in full. This version 1.0 SAP supersedes the statistical considerations identified in the protocol.

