8.7 Immunogenicity (Anti-BG00011 Antibodies)

Blood samples for the presence and titer of anti-BG00011 antibodies will be collected at scheduled visits of baseline, weeks 4, 12, 26, 38 and 60 (safety follow-up). The analysis visit should be defined using window in the table below in Table 4. Each blood sample will initially be tested for the presence of anti-BG00011 antibodies using a validated electrochemiluminescence (ECL) method. Confirmed positive samples using the screening assay will be titered and subsequently tested using a validated neutralization assay.

Table 4: Visit Windows for Anti-BG00011 Antibodies

Analysis Visit	Target visit day	Analysis visit window
Baseline (Day 0)	1	Most recent non-missing pre-dose value
Week 4	29	[2,57]
Week 12	85	[58,134]
Week 26	183	[135,225]
Week 38	267	[226,344]

Safety Follow-up (Week 60)	421	
 • If subject who discontinued treatment due to reasons other than study termination by sponsor: > min (393, study day of each subject's week 52/EOT visit in treatment period) * • If subject who discontinued treatment due to study early termination by sponsor: > min (393, study day of each subject's last dose)
-------------------------------	-----	---

* For subjects who discontinued the treatment due to reasons other than study termination by sponsor will go on to complete all scheduled visits until either week 52 or the study was terminated by sponsor due to the urgent safety measure whichever occurs first. The Week 52/EOT visit in treatment period is defined as the last visit scheduled for either week 52 or study termination due to the urgent safety measure.

Antibody results will be presented by treatment group and subject in listings. The incidence of antibodies to BG00011 will be summarized over time by treatment group using descriptive statistics.

Since the study early termination, the antibody results will not be included in the Part 1 data of the two-part database lock. The antibody data will be included in the Part 2 data. In order to keep the data integrity, the reconciliation of the antibody samples will be conducted prior to the Part 1 data being cleaned and finalized.

9 Pharmacokinetics (PK) Analysis

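### SAP 5.3 limits the immunogenicity population, without explanation, to subjects who screened antibody-negative on Day 0, so baseline prevalence and treatment-boosted antibody are never counted

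*SAP*

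**What the plan says.** Protocol 16.7.1, worded the same in versions 1 and 2, describes the immunogenicity population this way: "all subjects who were randomized and received at least 1 dose of study treatment and who have at least 1 postdose immunogenicity sample evaluated". It sets no condition on the baseline antibody result.

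SAP 5.3 starts from the MITT population (randomized and dosed), keeps the post-dose requirement, and adds that subjects must be those "whose pre-dose anti-BG00011 samples are screened negative at baseline (Day 0) visit". SAP 1 settles which text applies: "This version 1.0 SAP supersedes the statistical considerations identified in the protocol".

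SAP 8.7 describes the testing: "Each blood sample will initially be tested for the presence of anti-BG00011 antibodies using a validated electrochemiluminescence (ECL) method". It continues: "Confirmed positive samples using the screening assay will be titered and subsequently tested using a validated neutralization assay". One summary is planned: "The incidence of antibodies to BG00011 will be summarized over time by treatment group using descriptive statistics". Results are also to be listed by treatment group and subject. No treatment-induced or treatment-boosted category is defined, and there is no rule for what counts as a rise in titer.

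**The concern.** SAP 2 lists immunogenicity among the safety and tolerability endpoints, and SAP 1 undertakes to analyze safety data in full even though the trial stopped early. A population chosen by the baseline result of the same assay does not fit that undertaking well. Boosting can occur only in someone who already has antibody, and the SAP measures titers, yet that group is outside the one planned summary.

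The SAP does not acknowledge the change. SAP 5.1 explains how the MITT population relates to the protocol's ITT population, but SAP 5.3 says nothing about its departure from Protocol 16.7.1. A reader of the study report would see one incidence figure and could not tell how many subjects were left out, why, or what happened to their titers.

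**Working it through.** The documents state no antibody rate and no size for the immunogenicity population, so there is no figure to reproduce. The check is a comparison of texts, followed by an illustration under assumed rates.

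**1. What the SAP changes.** Both definitions require randomization, at least one dose and an evaluated post-dose sample (in SAP 5.3, subjects who "have at least 1 postdose immunogenicity sample evaluated for anti-BG00011 antibodies"). The Day 0 condition is the only addition.

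**2. Who is in, by baseline status** (given an evaluated post-dose sample):

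| Baseline status | Protocol 16.7.1 | SAP 5.3, literal reading |
|---|---|---|
| Negative on screen | in | in |
| Reactive on screen, not confirmed | in | out |
| Confirmed positive | in | out |
| No baseline sample | in | out |

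The third row needs no assumption: anyone with confirmed antibody at baseline is out on any reading. The second row depends on what *screened negative* means. If it is loose wording for a negative final result, those subjects stay in. The fourth row follows from the literal text. The schedule of events plans only one pre-dose antibody sample, at Day 0.

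**3. Link to the summary.** SAP 8.7 does not name its population. SAP 6.1 generally confines summaries to the relevant analysis population, and SAP 5.3 defines that population for immunogenicity. Table 4 in SAP 8.7 has a baseline row. If the summary uses the 5.3 population, baseline incidence is zero by construction.

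**4. Illustration.** Inputs: N = 145 per arm (SAP 4, planned enrollment). Assumed, not in the documents: baseline reactive proportion r = 1% to 20%; confirmed fraction c = 0 or 1; induced rate among subjects not confirmed positive i = 10%; boosted rate among confirmed positives b = 50%.

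- Excluded per arm = N × r
- Boosted cases not counted = N × r × c × b
- Induced-or-boosted incidence on the protocol population = i(1 − rc) + b·r·c
- Expected incidence on the SAP population = i = 10%

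| r | Excluded (145 × r) | Boosted, not counted (c = 1, b = 0.5) | Protocol-population incidence (c = 1) |
|---|---|---|---|
| 1% | 1.45 | 0.725 | 0.099 + 0.005 = 10.4% |
| 5% | 7.25 | 3.625 | 0.095 + 0.025 = 12% |
| 10% | 14.5 | 7.25 | 0.090 + 0.050 = 14% |
| 20% | 29 | 14.5 | 0.080 + 0.100 = 18% |

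The protocol-population incidence differs from the SAP figure by (b − i) × r × c. With c = 0 the difference is zero and only the denominator shrinks, for example 145 − 7.25 = 137.75 at r = 5%. With b > i the SAP figure is the lower one. With b < i it is the higher: at r = 5%, c = 1 and b = 0, the protocol population gives 0.095, or 9.5%, against 10%. The documents fix none of r, c, b or i, so they fix neither the size nor the sign.

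**The case against.** A baseline-negative denominator is a coherent choice for new, on-treatment antibody, and it parallels the treatment-emergence principle that SAP 8.2 applies to adverse events. Restoring the protocol population alone would not clearly improve matters, because an undifferentiated incidence would mix pre-existing with induced antibody. The summary is descriptive, and SAP 8.1 rules out testing of safety data. SAP 8.7 does not name the 5.3 population, while SAP 6.1 and 8.1 set MITT and safety populations as defaults unless otherwise specified.

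Much of this stands. The baseline-negative subset is worth keeping for induced antibody, and the population must be changed together with the categories. The point about unnamed populations carries less weight: SAP 5.3 is the specification that displaces the defaults, and 8.7 is the only unredacted section where it could apply.

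A reader might infer more than the texts allow:

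- **That antibody-negative subjects are wrongly excluded.** The documents do not say how a reactive, unconfirmed sample is classified. SAP 8.7 speaks of confirmed positives by the screening assay and describes no separate confirmatory assay. A count such as 7 of 145 per arm rests on an assumed 5% rate and on planned enrollment, in a trial that stopped early.
- **That reported incidence is biased downward.** That requires baseline-positive subjects to exist and to boost more often than others seroconvert.
- **That exposure or safety findings are weakened.** The inverse relation between antibody and exposure in Protocol 4.4.2.3 comes from monkeys after repeated dosing and does not concern pre-existing antibody. The PK and safety populations carry no antibody restriction.
- **That excluded subjects go unreported.** The by-subject listings name no population and may show them.

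**Conclusion.** The departure from Protocol 16.7.1 is real, unexplained and in force. On the natural reading that the 5.3 population serves the 8.7 summary, baseline prevalence and treatment-boosted antibody have no planned count, although titers are measured. This holds whatever the rates, but the number of subjects concerned is unknown and may be zero. The loss of unconfirmed-reactive subjects and of those with no baseline sample rests on the literal wording, which is ambiguous for the first group. The documents do not support any statement on the size or direction of an effect on reported incidence, and the table above only shows scale under assumed rates. This is a cheap improvement to a descriptive safety summary; no test or efficacy conclusion depends on it.

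**What to change.** In SAP 5.3, restore the protocol population: all dosed subjects with at least one evaluated post-dose antibody sample. Define baseline status by the final (confirmed) result rather than the screen.

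In SAP 8.7, name that population and report by arm:

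- baseline prevalence of confirmed antibody;
- treatment-induced antibody, with subjects not confirmed positive at baseline as the denominator and the handling of a missing baseline sample stated;
- treatment-boosted antibody, meaning confirmed positive at baseline with a titer rise above a stated threshold.

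Set the threshold before the Part 2 antibody data are seen, and preferably before the unblinding that follows Part I. SAP 1.1 allows a documented new version, and SAP 8.7 puts antibody results in Part 2 of the lock. Titers are already planned, so no new data are needed. The cost is some SAP wording, extra table rows and one more category to explain.

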5.4 Pharmacokinetic (PK) population

The pharmacokinetic (PK) population will include all safety subjects who have at least one PK concentration measurement. Subjects will be analyzed by the actual treatment received.

6 General Analysis

6.1 General Consideration

Data listings will be provided by treatment group, subjects and visits, if applicable. Summary statistics and statistical analyses will only be presented for data where detailed in this SAP and will generally only be performed for subjects included in the relevant analysis population. Unless otherwise specified, all variables will be summarized for the MITT population.

Summary statistics will be presented throughout for all endpoints at all visits including follow-up visits. For continuous variables, summary statistics will generally include number of subjects with data, mean, standard deviation (SD), median, minimum and maximum. In addition, the 95% confidence interval (CI) for the mean will be presented. For log-normal data the geometric mean and geometric coefficient of variation (CV) will also be presented. For categorical endpoints, summary statistics will generally include number and percentage of subjects with data in each category.

The statistical software, SAS®, will be used for all summaries and statistical analyses.

6.1.1 Analysis Visit and Study Day Definition

6.1.1.1 Baseline

Unless stated otherwise, baseline value is defined as the data collected prior to the time and/or on the date of first dose, which is usually the same day as the Baseline visit (Day 0). If there is more than one value on/before the date of the first dose, the non-missing value closest to the first dose will be used as the baseline value.

6.1.1.2 Analysis Visit

Observations that are collected after the first randomized dose as scheduled visit will be used to the corresponding analysis week.

6.1.1.3 Study/Treatment Day

To facilitate the analysis of the data in the treatment period (TP), study/treatment day will be calculated for each day in the study as the number of days between the date of the first randomized dose and the specific day of interest. For a day that is on or after the day of the first randomized dose, the study/treatment day is a positive value and will be calculated as (date of study day – date of the first randomized dose +1). For a day that is prior to the date of the first randomized dose, the study/treatment day is a negative value and will be calculated as (date of study day – date of the first randomized dose). The study starts at study/treatment day 1.

6.1.1.4 Early Termination or Unscheduled Visits for Acute Exacerbation of IPF

In general, when data are summarized by analysis visit, the Early Termination Visit or Unscheduled Visits for Acute Exacerbation of IPF will be assigned to an appropriate scheduled analysis visit by using a window scheme provided in Table 1.

Table 1: Visit Windows for Early Termination or Unscheduled Visits

Scheduled Visit Time	Target study day	Analysis visit window (days)	
		Efficacy & Safety Data	PK Data
Baseline (Day 0)	1	Most recent non-missing value on/before the date of first dose	
Day 5*	6	N/A	[6,7]
Week 4	29	[2,43]	[8,43]
Week 8	57	[44,71]	
Week 12	85	[72,99]	
Week 16	113	[100,127]	
Week 20	141	[128,162]	
Week 26	183	[163,203]	
Week 32	225	[204,246]	
Week 38	267	[247,288]	
Week 44	309	[289,337]	
Week 52	365	[338,393]	
Safety Follow-up (Week 60)	421	
 • If subject who discontinued treatment due to reasons other than study termination by sponsor: > min (393, study day of each subject's week 52/EOT visit in treatment period) ** • If subject who discontinued treatment due to study early termination by sponsor: > min (393, study day of each subject's last dose) 	

*The Day 5 Visit is for blood collection only (for PK analysis) and may be done in the clinic or at home (by appropriate personnel). Sample collection should occur on Day 5 (not sooner), with a +1 day window allowed (i.e., collection should occur on Day 5 but may occur on Day 6).

** For subjects who discontinued the treatment due to reasons other than study termination by sponsor will go on to complete all scheduled visits until either week 52 or the study was terminated by sponsor due to the urgent safety measure whichever occurs first. The Week 52/ EOT visit in treatment period is defined as the last visit scheduled for either week 52 or study termination due to the urgent safety measure.

The lower bound and the upper bound for the visit windows are defined as the midpoints of the scheduled visits. If the date and time from early termination visit or unscheduled visit for acute exacerbation falls in between the lower bound and the upper bound for a scheduled visit, then it will be assigned to that visit. If there are 2 or more assessments available in the same analysis window for a subject, the assessment that is closest to the target visit day will be used for analysis. If there are 2 or more assessments in the same analysis window with the same distance from the target visit day, the earlier/earliest assessment will be used.

6.2 Subject Disposition

The number and percentage of subjects who were randomized, dosed, randomized but not dosed, completed the study, discontinued study treatment (including reasons for discontinuation, specified in Sections 7.2.4) and withdrew from the study (including reasons for withdrawal, specified in Sections 7.2.5) will be summarized by treatment group and overall. The subject disposition will be summarized for the MITT and safety populations. If the safety population is the same as MITT population (i.e. all subjects receive their randomized treatment), the subject disposition will be summarized for MITT population only.

Additionally, a listing of subjects who discontinued treatment and/or withdrew from study and the associated reasons for discontinuation/withdrawal will be provided.

The number and percentage of subjects in each background stratum, treatment group and overall will be summarized for the MITT and safety populations. If the safety population is the same as MITT population, summary will only be presented for MITT population.

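### SAP 6.2 promises a randomised-but-not-dosed count by arm, but ties the disposition table to populations that contain only dosed subjects, so the row is zero by construction

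*SAP*

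**What the plan says.** SAP 6.2 lists the disposition items to be reported by treatment group and overall, beginning with "The number and percentage of subjects who were randomized, dosed, randomized but not dosed, completed the study" and going on to treatment discontinuation and study withdrawal with reasons. The population is then stated: "The subject disposition will be summarized for the MITT and safety populations". If the two populations coincide, "the subject disposition will be summarized for MITT population only". The background-stratum counts in the same section carry the same population rule. The section also provides "a listing of subjects who discontinued treatment and/or withdrew from study", with reasons, and names no population for that listing.

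SAP 5.1 defines the MITT set: it "population will include all subjects who are randomized and receive at least 1 dose of study treatment (BG00011 or placebo"). SAP 5.2 adds: "The safety population will include the same subjects as defined for the MITT population", regrouped by treatment actually received. The two remaining populations in SAP 5, immunogenicity and PK, are subsets of these. The SAP defines no all-randomised population.

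SAP 6.1 says that summaries "will generally only be performed for subjects included in the relevant analysis population", and sets a default: "Unless otherwise specified, all variables will be summarized for the MITT population".

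**The concern.** The disposition table is where a reader looks for subjects who were randomised and then left out of the efficacy set. The MITT rule is a post-randomisation exclusion, and SAP 7.1 makes MITT the default for every efficacy analysis. To judge whether the exclusion is balanced, a reader needs the number excluded and the reasons, by randomised arm. A row that must print zero is worse than a missing row, because it looks like an observed result. The study withdrawal and completion rows have a related difficulty: a subject can be randomised and leave before dosing, and a dosed-only denominator does not count that subject.

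**Working it through.** The plan gives no figure to reproduce. The check is set logic on the SAP's own definitions.

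1. MITT = randomised and dosed (SAP 5.1).
2. Safety = the same subjects as MITT, grouped by actual treatment (SAP 5.2).
3. The promised row = randomised and not dosed (SAP 6.2, opening sentence).
4. The intersection of (3) with (1) or with (2) is empty. The row is therefore 0 in each arm and overall.
5. Within either population, randomised and dosed are the same subjects, so both rows are 100% of the column.
6. The fallback to MITT alone leaves (4) and (5) unchanged.

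To show the effect, let u be the true number randomised but not dosed. The documents do not give u, so the values below are assumptions. The base of 290 is the planned number randomised (SAP 3). SAP 1 records that the study stopped early, so the number actually randomised may be lower. The MITT or safety table would show 290 − u randomised, 290 − u dosed and 0 not dosed. An all-randomised table would show 290, 290 − u and u, with percentage 100 × u / 290.

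| u (assumed) | MITT/safety: randomised / dosed / not dosed | All randomised: randomised / dosed / not dosed |
|---|---|---|
| 0 | 290 / 290 / 0 | 290 / 290 / 0 (0.0%) |
| 1 | 289 / 289 / 0 | 290 / 289 / 1 (0.3%) |
| 3 | 287 / 287 / 0 | 290 / 287 / 3 (1.0%) |
| 6 | 284 / 284 / 0 | 290 / 284 / 6 (2.1%) |
| 15 | 275 / 275 / 0 | 290 / 275 / 15 (5.2%) |

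The not-dosed entry in the middle column is the same for every u, so the table as specified carries no information about u. The only row where it is right is u = 0.

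The plausible size of u depends on the visit schedule. Protocol 7.2.2 places the eligibility recheck, randomisation, injection training and the supervised first dose at the Baseline visit, in that order. A subject can be lost between randomisation and injection, but the interval is short, so a small or zero count would be unsurprising.

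**The case against.** The best reply is that the sponsor plainly means to report this number. The opening sentence of SAP 6.2 names the row and asks for it by arm. The population sentence can be read as choosing between randomised and actual treatment, since its fallback applies when everyone received the assigned treatment. SAP 6.1 confines summaries to analysis populations only as a general rule, which leaves room for exceptions, and counting randomised subjects needs no named population. The layout of the tables is in the shells (SAP 1.2), which are not available here and may already use an all-randomised column.

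The point about intent stands: this is a wording conflict, and nothing suggests a decision to hide exclusions. It does not remove the conflict. The population sentence applies to the whole disposition summary and exempts no row. If the shells do use all randomised subjects, they disagree with the SAP text and one of the two still needs correcting.

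A reader might infer more than the documents support, in three ways.

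- That undosed subjects disappear from the report, or that this row is the only check on the exclusion. The SAP 6.2 listing states no population, so an undosed subject recorded as withdrawn could appear there. Protocol 9.1 can also be read to class such a subject as a screen failure, with the reason documented. Neither route promises a count by arm, but the stronger claim fails, and the unseen shells are a further reason not to say that the report cannot show the number.
- That every discontinuation percentage has the wrong base. Protocol 10.1 defines treatment discontinuation as the premature ending of dosing. An undosed subject has no dosing to end, so a dosed denominator is right for that row. Only study withdrawal and completion belong on the all-randomised base.
- That a definite number is missing, for example 1% to 3% of 290, or about 3 to 9 subjects (2.9 and 8.7 before rounding). No passage supports that rate, the range leaves out zero, and 290 is a plan that early termination may have cut short.

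**Conclusion.** The contradiction holds on the SAP's own definitions and needs no outside fact. As written, the row is zero and randomised equals dosed in every arm, and no other part of the SAP text repairs it. The consequence is limited to reporting and traceability: the primary estimate, the other efficacy analyses and the safety rates are unaffected. The number of subjects concerned is unknown and may be zero. The finding is minor. It assumes that the population sentence in SAP 6.2 governs all the disposition rows, which is its plain reading, and that the shells do not silently override it, which cannot be checked here.

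**What to change.** In SAP 6.2, replace the population sentence so that:

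- the randomised, dosed, randomised-but-not-dosed (with reason), completed and withdrew-from-study rows are tabulated for all randomised subjects, by randomised arm and overall;
- the background-stratum counts use the same base;
- the numbers in the MITT and safety populations appear as rows of that table;
- treatment discontinuation and its reasons keep the dosed (MITT or safety) denominator.

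The table shells should be brought into line. The cost is about one SAP sentence plus a check of the shells. Randomisation runs through the interactive response system (Protocol 9.2), so the assignments should already be held. No new data and no change to any analysis are needed.
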